4.3 Dose Escalation/De-escalation

If a DLT occurs in 2 or more patients on a dose level during the first cycle, the MTD will be exceeded and we will consider this dose level to be intolerable. If a DLT occurs in 1 of 3 patients during this time, an additional 3 patients will be enrolled at that dose level cohort and evaluated for DLT before dose escalation can proceed. If no other patient in the cohort has a DLT, escalation to the next cohort may proceed 1 week later from the last included patient on the current cohort. If a second patient in a cohort has a DLT, MTD determination will then be conducted by one of the following schemes:

- If ≥ 2 of 3 patients in cohort 1 exhibit a DLT at the dose of 1.5 mg/kg CT-011 in combination with lenalidomide 15 mg, 3 more patients will be enrolled at a de-escalated dose level cohort. This de-escalation cohort (Cohort -1) will use the same dose of CT-011 (1.5 mg/kg) in combination with 10 mg lenalidomide. If no further DLTs are observed, we will consider dose escalation of the CT-011 with this lower dose of lenalidomide such that the dose escalation of CT-011 to 3 mg/kg with lenalidomide 10 mg will proceed in the next cohort. However, if ≥ 2 patients experience DLT with CT-011 1.5 mg/kg and lenalidomide 10 mg, then we will further de-escalate lenalidomide to 5 mg and enroll 3 more patients on CT-011 1.5 mg/kg combined with lenalidomide 5 mg. The same criteria for MTD will be used for these de-escalation dose level cohorts.
- If ≥ 2 patients in cohort 2 exhibit a DLT at the dose of 3 mg/kg CT-011 in combination with lenalidomide 15 mg, we will explore tolerability of an intermediate dose level of lenalidomide, where 3 patients will be enrolled and treated with 3 mg/kg of CT-011 in combination with 10 mg lenalidomide. The dose escalation of CT-011 to 6 mg/kg with lenalidomide 10 mg will proceed in the next cohort if no more than one DLT is observed in the 3 mg/kg CT-011+10mg lenalidomide cohort.
- If ≥ 2 patients in cohort 3 exhibit a DLT at the dose of 3 mg/kg CT-011 in combination with lenalidomide 25 mg, 3 more patients will be enrolled at the 3 mg dose of CT-011 in combination with 15 mg lenalidomide. If there is < 1 DLT with CT011 3mg/kg and lenalidomide 15 mg, this will be defined as the MTD. If there are 2 or more DLT, then 3 additional patients will be enrolled at the CT-011 3mg/kg and lenalidomide 10 mg, which will become the MTD.

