- If ≥ 2 patients in cohort 4 exhibit a DLT at the dose of 6 mg/kg CT-011 in combination with lenalidomide 25 mg, 3 more patients will be enrolled at the 6 mg dose of CT-011 in combination with 15 mg lenalidomide. If there is < 1 DLT with CT011 6mg/kg and lenalidomide 15 mg, this will be defined as the MTD. If there are 2 or more DLT, then 3 additional patients will be enrolled at the CT-011 6mg/kg and lenalidomide 10 mg, which will become the MTD

To determine dose escalation, we will focus on the number of patients who experience dose limiting toxicity; i.e. a patient who experiences more than one DLT will be counted only once.

Discontinuation of treatment due to disease progression will not constitute a DLT.

In the Phase 1 portion of the study, subjects who withdraw or prematurely discontinue treatment before completing the first treatment cycle for reasons other than toxicity and DLT will be replaced.

After 4 cycles of therapy or earlier if clinically indicated, response determination will be assessed by the IMWG criteria. At the end of Cycle 4, if a subject has responded (complete or partial response) or has stable disease, dosing with CT-011, lenalidomide and dexamethasone(if initiated after cycle 1-2) will continue for a minimum of 8 additional cycles or until withdrawal.

For the Phase II portion

Upon determination of the MTD in the phase I portion of this trial, the phase II portion of the study will commence enrollment at the MTD determined in the phase I portion with CT-011 in combination with lenalidomide. In the event that a MTD is not established, safety and tolerability data collected in the Phase I portion of the study will guide decisions on dosing of CT-011 in the phase II trial.

Dexamethasone 40 mg orally weekly may be added if only stable disease after 3 cycles according to the IMWG criteria (section13). Dexamethasone can be reduced to 20 mg based on tolerability or if patient is 70 years or older.

During the phase II portion of this trial, we will not evaluate patients for DLTs as was done in the phase I portion; however, we will use the DLT criteria to identify potential toxicity and tolerability concerns occurring at any cycle to initiate further evaluation to ensure safety of patients. An independent Data and Safety Monitoring Committee will continue oversight of this trial. See Appendix E for details.

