6.0 STATISTICAL CONSIDERATIONS

6.1 Overview of study design

This is a phase I/II clinical trial designed to first determine the MTD of the combination of CT-011 + lenalidomide in relapsed/refractory MM patients and then to assess the associated efficacy of this regimen in this patient population through evaluation of the overall response rate. The phase I portion follows the standard cohorts-of-3 phase I clinical trial design, and the phase II portion will utilize a one-stage three outcome phase II design (Sargent et al, 2001).

6.1.1 *Phase I portion*

In the phase I portion, we will assess the MTD using a standard cohorts-of-3 phase I trial design, where the MTD is defined as the dose level at which no more than one of 6 patients experiences a dose-limiting toxicity (DLT). The dose escalation rules follow the standard design, where cohorts of 3 are accrued to a dose level and evaluated for DLT before making a decision to dose escalate or not. If in the first 3 patients on a dose level there are no DLTs observed, the next cohort of 3 can be accrued to the next dose level. If one DLT of the first 3 patients at a dose level experiences DLT, then 3 additional patients will be accrued to that dose level to ensure it is tolerable and does not exceed the MTD. Any dose that has two or more patients with DLTs has exceeded the MTD and is deemed to have unacceptable toxicity. If the first dose level proves to have unacceptable toxicity (i.e. 2+ DLTs), then 3-6 patients will be accrued to the de-escalation dose level (dose level -1). For this portion of the trial, we expect a minimum of 12 patients (worst case scenario of 2+ DLTs on dose level cohorts 1, -1, and -2) and a maximum of 30 patients (e.g. 6 at each of the 4 dose levels and an intermediate dose level). Adverse events and toxicities will be summarized using the NCI CTCAE version 4 and based on severity and perceived attribution to study treatment; these outcomes will be assessed and tabulated by dose level.

6.1.2 *Phase II portion*

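### The cohort 3 and cohort 4 fallback rules state no outcome for exactly one DLT patient, conflict with the plan's own MTD definition, and leave unclear whether cohort 2 patients count

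*Combined protocol and SAP*

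**What the plan says.** Section 4.3, repeated in the synopsis under Dosing Regimen, opens with a general rule. One DLT patient among the first three brings three more patients at that level. "If no other patient in the cohort has a DLT, escalation to the next cohort may proceed 1 week later". Two or more make the level intolerable. Section 6.1.1 repeats these steps and sets the limit: "the MTD is defined as the dose level at which no more than one of 6 patients experiences a dose-limiting toxicity (DLT"). Section 2.3 uses the same limit and calls the MTD the highest such combination.

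Separate branches then follow for each failed cohort.

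- **Cohort 3.** The trigger is "If ≥ 2 patients in cohort 3 exhibit a DLT at the dose of 3 mg/kg CT-011 in combination with lenalidomide 25 mg". Then "3 more patients will be enrolled at the 3 mg dose of CT-011 in combination with 15 mg lenalidomide", and "If there is < 1 DLT with CT011 3mg/kg and lenalidomide 15 mg, this will be defined as the MTD". With two or more DLTs, three patients are treated at 3 mg/kg with 10 mg, which the text names as the MTD.
- **Cohort 4.** The form is the same at the higher CT-011 dose: "If there is < 1 DLT with CT011 6mg/kg and lenalidomide 15 mg, this will be defined as the MTD". Two or more DLTs lead to 10 mg.
- **Cohort 2.** The trigger is "If ≥ 2 patients in cohort 2 exhibit a DLT at the dose of 3 mg/kg CT-011 in combination with lenalidomide 15 mg", so cohort 2's combination is the one re-tested after cohort 3 fails. This branch drops lenalidomide to 10 mg. After that, "The dose escalation of CT-011 to 6 mg/kg with lenalidomide 10 mg will proceed in the next cohort if no more than one DLT" is seen at 3 mg/kg with 10 mg.

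The synopsis, under Study Design, has a different rule: after DLTs in 2 of 6, the MTD is the next level down. It mentions no re-test.

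**The concern.** DLTs are counted by patient, so fewer than one means none. The cohort 3 and cohort 4 branches therefore cover 0, 2 and 3 DLT patients and skip 1, the count on which a 3+3 design most needs an instruction. The literal threshold of zero is also stricter than both the general 1-of-3 expansion and the 1-of-6 definition, and stricter than the limit of one in the cohort 2 branch.

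The cohort 3 branch has a further problem. It returns to a combination that already has three or six evaluated patients, and does not say whether they enter the count.

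The MTD is the phase I primary endpoint and fixes the phase II regimen. Sections 5 and 6.1.2 also carry six patients treated at the MTD into the phase II total of 29 (6 + 23). Which combination is declared, and how many patients stand behind it, therefore matters beyond phase I.

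**Working it through.** **Planning figure.** The stated phase I maximum of 30 reproduces from the plan's own example: (4 levels + 1 intermediate) × 6 = 30. It does not settle the rule.

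**Cohort 2 history.** Cohort 3 opens only after cohort 2 shows 0/3, or 1/3 followed by 0/3, which is 1/6. These are the only two starting points for the cohort 3 fallback.

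**Every count under two readings of the branch:**

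| Cohort 2 | New DLT patients of 3 | New patients only | All patients at the combination |
|---|---|---|---|
| 0/3 | 0 | MTD | 0/6: MTD |
| 0/3 | 1 | none stated | 1/6: none stated, yet meets at most 1 of 6 |
| 0/3 | 2 or 3 | go to 10 mg | 2/6 or 3/6: go to 10 mg |
| 1/6 | 0 | MTD | 1/9: cannot be below one, none stated |
| 1/6 | 1 | none stated | 2/9: two or more, go to 10 mg |
| 1/6 | 2 or 3 | go to 10 mg | 3/9 or 4/9: go to 10 mg |

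The readings differ in both rows with a 1/6 history and at most one new DLT. Each reading leaves at least one count without an outcome. The cohort 4 fallback (6 mg/kg with 15 mg) is not one of the scheduled dose levels, so only the missing count arises there.

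**Synopsis against Section 4.3.** The level below cohort 3 is 3 mg/kg with 15 mg. The synopsis makes it the MTD at once after 2 of 6; Section 4.3 re-tests it and may move to 10 mg. The level below cohort 4 is 3 mg/kg with 25 mg, but Section 4.3 goes to 6 mg/kg with 15 mg.

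**Chance of the missing count.** For a true DLT rate p at the fallback combination (assumed), P(exactly 1 of 3) = 3p(1−p)²:

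- p = 5%: 3 × 0.05 × 0.9025 = 0.135
- p = 10%: 3 × 0.10 × 0.81 = 0.243
- p = 20%: 3 × 0.20 × 0.64 = 0.384
- p = 25%: 3 × 0.25 × 0.5625 = 0.422
- p = 30%: 3 × 0.30 × 0.49 = 0.441

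These are conditional on reaching the fallback.

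**Chance per trial, cohort 3 branch.** A level passes with probability (1−p)³ + 3p(1−p)² × (1−p)³, which is 0.973, 0.906, 0.709, 0.494 and 0.309 at 5%, 10%, 20%, 30% and 40%. The event is: cohorts 1 and 2 pass, cohort 3 fails, and exactly one new DLT follows. For assumed rates in cohorts 1/2/3:

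- 5/10/20%: 0.973 × 0.906 × (1 − 0.709) × 0.243 = 0.062
- 10/20/30%: 0.906 × 0.709 × (1 − 0.494) × 0.384 = 0.125
- 20/30/40%: 0.709 × 0.494 × (1 − 0.309) × 0.441 = 0.107

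**How far the threshold matters.** If the three new patients must have no DLT, 3 mg/kg with 15 mg qualifies with probability (1−p)³ = 0.729, 0.512 and 0.343 at 10%, 20% and 30%. If the general 1-of-3 expansion applies to the fallback as a fresh evaluation, the probabilities are 0.906, 0.709 and 0.494. The differences are 0.177, 0.197 and 0.151.

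**The case against.** The strongest reply is that the plan already supplies the missing step. The opening of Section 4.3, and Section 6.1.1, say that 1 of 3 brings three more patients, and neither excludes fallback levels. The zero threshold may be a slip for at most one, since it stands opposite two or more and near a branch that allows one. This stands in part: a reader might infer that the plan has no rule at all for one DLT, and that goes too far. But neither branch invokes the general rule, whereas the cohort 1 branch expressly carries the MTD criteria over to its de-escalation cohorts. Correcting a slip would also leave 1/6 plus 1/3 unresolved.

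A reader might also infer that cohort 2's data are discarded. The documents do not say so; they are silent. The added three may be meant to fill a 0/3 cohort 2 to the six that Sections 5 and 6.1.2 expect at the MTD. At assumed rates of 10% to 30%, a passing cohort 2 has 0/3 in 1/(1 + P(1 of 3)) = 80% to 69% of cases. In the rest it already has six patients, and a cumulative count below one is impossible. The text is ambiguous; it does not show that data are unused.

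Finally, failing cohort 2 can lead to CT-011 6 mg/kg, while failing cohort 3 ends at 3 mg/kg. A reader might call this an error. The asymmetry is real, but a two-drug escalation may follow a fixed path, and nothing in the text requires equal ceilings. It is mainly a design choice; what needs attention is the wording of Section 2.3.

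**Conclusion.** The point holds as a defect of wording in rules that decide the phase I primary endpoint. Exactly one DLT patient has no outcome in the cohort 3 and cohort 4 branches. Their literal threshold contradicts the 1-of-3 expansion and the 1-of-6 definition. The cohort 3 branch does not say who is counted, and the synopsis gives a different rule after 2 of 6.

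The size rests on assumed DLT rates, because the documents give none: about 14% to 44% for rates of 5% to 30%, once the fallback is reached. Those figures should not be read as the chance for the trial as a whole, which is about 6% to 12.5% for the cohort 3 branch in the three scenarios shown. The difference in CT-011 ceilings is a secondary note.

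**What to change.** Reconcile the synopsis (Study Design and Dosing Regimen) and the Section 4.3 branches with Sections 2.3 and 6.1.1:

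- Give each count of 0, 1, 2 and 3 DLT patients an outcome in the cohort 3 and cohort 4 fallbacks, consistent with the protocol's own MTD definition.
- State which patients at the combination are counted. If cohort 2 patients are included, say how a limit of 1 in 6 applies to nine patients.
- Settle whether a failed cohort leads to the level below or to the branch.
- Reconcile the CT-011 ceilings of the cohort 2 and cohort 3 branches with Section 2.3, or describe the cohort 3 result as the highest among the combinations tested.

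The choice of rule and doses is for the investigators. The cost is an amendment to the text. Clarifying the count or the label adds no patients. If the investigators apply six-patient expansion to every fallback level, the maximum needs a check: the cohort 3 path gives 3 × 6 + 2 × 6 = 30, within the stated limit, but the cohort 4 path could reach 4 × 6 + 2 × 6 = 36.

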Patients that experience a lenalidomide-related hematologic DLT may continue on therapy if the event resolves, the investigator considers it in the best interest of the patient to continue and the patient qualifies for initiation of the next cycle with standard of care lenalidomide dose reduction. However, the DLT will count towards establishment of maximally tolerated dose (MTD). A cohort will be expanded if 1 of 3 pts experiences a DLT. If 2 of 6 pts on a cohort experience a DLT, then MTD will be determined as the dose level immediately below that in which 2 of 6 pts experience a DLT. The Phase II portion of the trial will commence upon completion of the Phase I portion. In the event that a MTD is not established, safety and tolerability data collected in the Phase I portion of the study will guide decisions on dosing of CT-011 in the phase II trial.

The maximum tolerated dose level (MTD) combination is defined as the dose level at which no more than one of six patients experiences a DLT as defined above. Any dose level that has two or more DLTs reported is considered to exceed the MTD and not be a tolerable dose level. Dose escalation will be determined based on the occurrence of DLTs observed in the first cycle of therapy. For the purposes of dose determination, DLTs will be counted by patient, i.e., a patient who experiences more than one DLT will be counted only once.

Discontinuation of treatment due to disease progression will not constitute a DLT. In the phase I portion of this trial, if a patient goes off treatment before completing cycle one for reasons other than toxicity or DLT, they will be replaced at that dose level to fully evaluate the tolerability of this regimen at that dose level.

After 4 cycles of therapy or earlier if clinically indicated, response determination will be assessed by the IMWG criteria. At the end of Cycle 4, if a subject has responded (complete or partial response) or has stable disease, dosing with CT-011 and lenalidomide will continue for a minimum of 8 additional cycles or until withdrawal.

If disease progression is observed at the end of Cycle 4 evaluation, all study therapy will be discontinued. Confirmation of progression of disease will be done according to the IMWG criteria.

Following the 30-day post-treatment follow-up assessment, additional evaluations will occur once per month (unless subject discontinued due to progression) until

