the earliest of the following events: disease progression, the time of initiation of new therapy, death or study completion.

Study completion is defined as 30 days after the last subject remaining on study medication discontinues study medication.

For the Phase II portion

Upon completion of the cohorts in phase I, the phase II portion of the study will commence utilizing the planned target doses (or MTDs determined) with CT-011 in combination with lenalidomide and dexamethasone

During the phase II portion of this trial, we will not evaluate patients for DLTs as was done in the phase I portion; however, we will use the DLT criteria to identify potential toxicity and tolerability concerns occurring at any cycle to initiate further evaluation to ensure safety of patients. An independent Data Monitoring Committee will continue oversight of this trial.

Treatment will continue until Progression of disease, death, unacceptable toxicity or patient or treating physician decision to discontinue therapy.

Dosing Regimen

Dosing cohorts for the phase I study: We will conduct a standard 3+3 design over 4 dose levels of 1.5, 3, 3, and 6 mg/kg of CT-011 given intravenously every 4 weeks (28 days) on day 3, and lenalidomide given at 15, 15, 25, and 25 mg orally daily on days 1-21 of a 28-day cycle. The study drug CT-011 and lenalidomide can move independently of one another as described in the Table below. Dexamethasone 40 mg orally weekly may be added if only stable disease after 3 cycles according to the IMWG response criteria (section 13-0). Dexamethasone can be reduced to 20 mg based on tolerability or if patient is 70 years or older.

A minimum of 3 patients to a cohort with at least one week break between cohorts.

	CT-011- mg/kg day 3
Cohort -1	1.5
Cohort -2	1.5
Cohort 1	1.5
Cohort 2	3
Cohort 3	3
Cohort 4	6

	Lenalidomide- mg Days 1-21
Cohort -1	10
Cohort -2	5
Cohort 1	15
Cohort 2	15
Cohort 3	25
Cohort 4	25

If a DLT occurs in 2 or more patients during the first cycle, we will consider this

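### Section 4.3 can declare an MTD after three patients, in two branches with no DLT limit, although the MTD definition and the 29-patient analysis assume six

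*Combined protocol and SAP*

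**What the plan says.** The MTD is defined on six patients, at most one with a DLT (synopsis, Primary Endpoint; sections 2.3 and 6.1.1). Sections 5 and 6.1.2 carry the six phase I patients treated at the MTD into the primary analysis and add 23, giving 29. Sections 4.3 and 6.1.1 say that two or more DLTs mean a level exceeds the MTD.

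Expansion from three to six has a single trigger. In the synopsis: "A cohort will be expanded if 1 of 3 pts experiences a DLT". Sections 4.3 and 6.1.1 agree.

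The branches in section 4.3, repeated in the synopsis, then read:

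- Cohort 4 exceeded, first step: "If there is < 1 DLT with CT011 6mg/kg and lenalidomide 15 mg, this will be defined as the MTD".
- Cohort 4 exceeded, second step, after two or more DLTs at the first: "3 additional patients will be enrolled at the CT-011 6mg/kg and lenalidomide 10 mg, which will become the MTD".
- Cohort 3 exceeded, second step: "3 additional patients will be enrolled at the CT-011 3mg/kg and lenalidomide 10 mg, which will become the MTD".
- Cohort 2 exceeded: "The dose escalation of CT-011 to 6 mg/kg with lenalidomide 10 mg will proceed in the next cohort if no more than one DLT" is seen at 3 mg/kg + 10 mg. What follows 0 of 3 at 6 mg/kg + 10 mg is not stated.

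If cohort 4 itself clears, section 4.3 offers only a general sentence: "In the event that a MTD is not established, safety and tolerability data collected in the Phase I portion of the study" are to inform the phase II dose of CT-011. The synopsis also allows phase II to start at target doses that it does not define.

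**The concern.** Phase II starts once an MTD is determined, and nothing sets a minimum number of patients at that dose. The explicit branches can therefore name an MTD on half the patients that the definition requires. In the two 10 mg end branches, the words used would name an MTD even if two or three of the three patients had a DLT. The cohort 3 and 4 branches also give no outcome for exactly one DLT at the 15 mg step: one sentence covers fewer than one, the next covers two or more.

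At stake is the choice of dose at which 23 further patients are treated. A smaller matter is the primary analysis. Three carried over plus 23 is 26, while the cutoffs are given only for 29 evaluable patients. The synopsis caps new phase II patients at 23, and no rule restores 29.

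**Working it through.** **1. The plan's own figures.** Inputs from section 6.1.2: null response rate 0.25, alternative 0.50, n = 29, not promising at ≤ 9, promising at ≥ 12. Exact binomial:

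- type I error, P(X ≥ 12 | 0.25) = 0.039 (stated 4%)
- type II error, P(X ≤ 9 | 0.50) = 0.031 (stated 3%)
- eta, P(X ≤ 9 | 0.25) = 0.834 (stated 0.83)
- pi, P(X ≥ 12 | 0.50) = 0.868 (stated 0.87)

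All four reproduce, so the design is sound if six patients are carried over.

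**2. With three carried over, n = 26.**

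- Cutoffs re-derived to ≤ 8 and ≥ 11: type I 0.040, type II 0.038, eta 0.820, pi 0.837.
- Cutoffs left at 9 and 12: type I 0.016, type II 0.084, eta 0.909, pi 0.721.

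**3. Which doses are affected.** The first step down from cohort 3, 3 mg/kg + 15 mg, is the cohort 2 dose. Three more patients bring it to at least six, so it is not affected. The doses that can end on three are 6 mg/kg + 15 mg, 3 mg/kg + 10 mg, 6 mg/kg + 10 mg, and cohort 4 itself.

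**4. How often.** The documents give no DLT rate, so assume one rate p at every level. Let

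- A = (1−p)³ + 3p(1−p)⁵, the chance that a level passes 3+3
- z = (1−p)³, the chance of 0 of 3
- g = 3p²(1−p) + p³, the chance of two or more DLTs in three patients
- s = (1−p)⁶ + 6p(1−p)⁵, the chance of at most 1 of 6

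| p | A | z | g | s |
|---|---|---|---|---|
| 0.10 | 0.906 | 0.729 | 0.028 | 0.886 |
| 0.20 | 0.709 | 0.512 | 0.104 | 0.655 |
| 0.30 | 0.494 | 0.343 | 0.216 | 0.420 |

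Chance that phase II starts with three patients at its dose, by route:

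| Route | Formula | p = 0.10 | p = 0.20 | p = 0.30 |
|---|---|---|---|---|
| Explicit: 6 mg/kg + 15 mg on 0 of 3 | A³(1−A)z | 0.051 | 0.053 | 0.021 |
| Explicit: either 10 mg end branch | (A³+A²)(1−A)g | 0.004 | 0.026 | 0.040 |
| **Explicit total** | | **0.055** | **0.079** | **0.061** |
| Permitted: cohort 4 clears at 0 of 3 | A³z | 0.542 | 0.182 | 0.041 |
| Permitted: 6 mg/kg + 10 mg after cohort 2, 0 of 3 | A²(1−A)z | 0.056 | 0.075 | 0.042 |
| **All routes** | | **0.654** | **0.336** | **0.145** |

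The end-branch row counts DLTs among the three added patients only. Paths in which cohort 1 is exceeded are left out; there the text says the same MTD criteria apply.

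**5. How often six patients would change the decision.** After 0 of 3, three more patients reject the level with probability g. An end-branch level fails the definition with probability 1 − s.

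- p = 0.10: (0.542 + 0.051 + 0.056) × 0.028 + 0.004 × 0.114 = 0.019
- p = 0.20: (0.182 + 0.053 + 0.075) × 0.104 + 0.026 × 0.345 = 0.041
- p = 0.30: (0.041 + 0.021 + 0.042) × 0.216 + 0.040 × 0.580 = 0.046

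**The case against.** **The general rules govern the branches.** Section 4.3 opens by calling any level with two or more DLTs intolerable, and section 6.1.1 repeats this. Read together, the missing DLT limit is a drafting conflict. That is a fair reading, and it would be unsafe to conclude that the trial would knowingly adopt a failed dose. But the sentence applying the same MTD criteria appears only in the cohort 1 scheme. The general rules also trigger no expansion after 0 of 3.

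**Not expanding after 0 of 3 is ordinary 3+3 practice, and section 6.1.1 mentions six per level.** The first part is true of the escalation rule. This plan, however, writes six into its MTD definition and its primary analysis. The mention in section 6.1.1 is an example explaining the maximum of 30 and requires nothing.

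**The 65% figure is not a finding about the text.** This stands. A reader might infer that phase II would usually open on three patients. Most of the 65% is cohort 4 clearing at 0 of 3, where the dose is left to judgement; the text neither directs opening at three nor forbids adding three. The cohort 2 route is likewise silent, since it never calls 6 mg/kg + 10 mg the MTD.

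**The synopsis has another rule.** After 2 of 6 DLTs, "then MTD will be determined as the dose level immediately below that in which 2 of 6 pts experience a DLT". That conflicts with the cohort 3 and 4 schemes and does not cure the problem, because the level below may itself have cleared at 0 of 3.

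**The flat rate is artificial.** It ignores any fall in toxicity as lenalidomide is cut from 25 to 15 to 10 mg. Dose-dependent rates could move the figures either way.

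**Phase II is monitored.** Section 4.3 applies the DLT criteria at any cycle to trigger evaluation, under an independent committee, and Appendix E adds regular safety review. This limits the harm but does not replace choosing the dose by the stated definition.

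**Conclusion.** The point holds as a contradiction within the plan. Three doses can be declared the MTD on three patients, two of them with no DLT limit, against the plan's own definition, its two-or-more rule and the six patients in its analysis. Alongside it is a gap: no rule brings a final dose cleared at 0 of 3 up to six.

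The size is modest. Under flat rates of 10% to 30%, the explicit branches arise in roughly 5% to 8% of trials, and requiring six would overturn the chosen level in roughly 2% to 5%. The larger all-route frequencies describe what the text allows.

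The efficacy consequence is secondary. A reader might infer that pi drops from 0.87 to 0.72. That happens only if the 29-patient cutoffs are applied unchanged to 26 patients, which the plan does not say. With cutoffs re-derived for 26, pi is 0.84 and type II error 3.8%. These figures assume that all 26 are evaluable.

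The text should be changed before dose selection, because the correction is cheap and concerns the primary phase I endpoint.

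**What to change.** State one gate for every path: phase II opens only at a level where at least six patients have been treated and at most one had a DLT. Then:

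1. In the cohort 3 and cohort 4 branches, replace both MTD declarations (15 mg and 10 mg steps) with the gate. This also settles the case of exactly one DLT. At 3 mg/kg + 15 mg, count the cohort 2 patients.
2. Expand any final level cleared at 0 of 3 to six, including cohort 4 and 6 mg/kg + 10 mg after the cohort 2 branch. Define the synopsis target dose as 6 mg/kg + 25 mg for the case where cohort 4 clears.
3. If the 10 mg step fails, fall back to the highest level already cleared, also at six: 3 mg/kg + 25 mg after the cohort 4 branch, 1.5 mg/kg + 15 mg after the cohort 3 branch. If 6 mg/kg + 10 mg fails in the cohort 2 branch, use 3 mg/kg + 10 mg. If that level fails on expansion, take the next lower cleared level; if none qualifies, phase II does not open.
4. Align the synopsis rule on the level immediately below with this.

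Cost: three more patients at the chosen level, already counted in the 29, and about one extra 28-day cycle. The longest path needs 24 + 6 + 6 = 36 in phase I, so the cap of 30 must be amended. The present text already reaches 30 to 33 there (24 + 3 or 6, + 3). In 200,000 simulated trials per rate under the gate, phase I exceeded 30 in 0.1%, 0.6% and 0.7% at flat rates of 10%, 20% and 30%.
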